13.6.2.1 Sensitivity Analysis for the Primary Endpoint

Blinded Phase:

The following sensitivity analyses will be conducted for the primary endpoint for the blinded phase:

- Wilcoxon rank-sum test on percentage change from baseline in seizure frequency during the treatment period. An estimate of the median differences between each GWP42003-P group and placebo, together with approximate 95% CIs, will be calculated using the Hodges–Lehmann approach.
- Primary endpoint analysis repeated using the PP analysis set.
- Primary endpoint analysis repeated using the maintenance period (Day 29 to the end of the evaluable period) rather than the treatment period.
- Primary endpoint analysis repeated using the worst case of last observation carried forward (LOCF), next observation carried backward (NOCB) and the mean from the non-missing data for each patient to impute missing data arising from unreported days in IVRS.
 - Any intermittent missing data for the number of seizures arising from unreported days in IVRS will be imputed using the worst (highest number of seizures) of the following for each patient: LOCF, NOCB and the mean daily number of seizures during the treatment period based on non-missing data:

$$\text{Number of seizures} \div \text{Number of reported days in IVRS.}$$
- A rank ANCOVA on percentage change from baseline in number of seizures (average per 28 days) during the treatment period.
 - The ranks of the percentage change from baseline and the baseline number of seizures (average per 28 days) will be calculated. The rank of the percentage change from baseline will then be analyzed using an ANCOVA model with the rank of the baseline number of seizures (average per 28 days) and age group (1–6 years, 7–11 years, 12–17 years and 18–65 years) as covariates and treatment group as a fixed factor. The estimated least squares means, treatment differences, together with the 95% CIs and p-value will be presented.
- ANCOVA of log transformed number of seizures (average per 28 days) during the treatment period.

Study Code: GWEP1521
EudraCT Number: 2015-002154-12
Protocol V8 23Apr19

- The number of seizures (average per 28 days) during the treatment period and the baseline number of seizures (average per 28 days) will be log transformed prior to analysis. The log transformed number of seizures (average per 28 days) during the treatment period will then be analyzed using an ANCOVA model with the log transformed baseline number of seizures (average per 28 days) and age group as covariates and treatment group as a fixed factor. The back transformed estimated treatment ratios, together with the 95% CIs and p-value will be presented.
- If there are any patients with no seizures post-baseline, then 1 will be added to the number of seizures (average per 28 days) for all patients prior to log transformation.
- Primary endpoint analysis repeated using each 4 weeks of the maintenance period (Week 1 to 4, Week 5 to 8 and Week 9 to 12 of the 12-week maintenance period) rather than the treatment period.
 - This analysis will include only patients who have at least 7 days of seizure data within each corresponding 4-week period.
- Wilcoxon rank-sum test on percentage change from baseline in number of seizures (average per 28 days) during the treatment period, using multiple imputation (MI) to impute data under the Missing Not at Random (MNAR) assumption.
 - MNAR will be assumed for missing values resulting from two scenarios, discontinuation due to AEs, and discontinuation due to any reason in the GWP42003-P dose groups and missing at random (MAR) for others, including other patients discontinued in the GWP42003-P dose groups and patients in the placebo group.
 - MI will be performed on the seizure frequency, based on time points corresponding to each 14 calendar days of the treatment period. Intermittent missing values for intermediate 14-day time points before the last 14-day time-point will be imputed using the MCMC method in SAS PROC MI with an IMPUTE=MONOTONE statement for 100 times for each treatment group separately. Then, monotone missing data assumed under the MAR assumption at time-point *t* (i.e., patients in the placebo group and patients in the GWP42003-P groups who did not discontinue due to AEs or for any reason) will be imputed using the MI procedure with the ‘MONOTONE REG’ option, for each treatment group separately. The

Study Code: GWEP1521
EudraCT Number: 2015-002154-12
Protocol V8 23Apr19

imputation model will include baseline seizure frequency and each 14-day time-point up to time-point t (in chronological order). With the data imputed from above, monotone missing data of patients in the GWP42003-P groups under the MNAR assumption will be imputed. At each 14-day time-point t , the input dataset for the MI procedure will include all placebo patients and those patients from the GWP42003-P groups that have values missing under MNAR at that time-point. The imputation model will include seizure frequency at baseline and each 14-day time-point up to time-point t (in chronological order) and will be performed for each GWP42003-P group separately.

Full details for this sensitivity analysis will be provided in the SAP.

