13.1 Sample Size, Power and Significance Levels

Blinded Phase:

A total of 210 patients will be enrolled. The 210 patients will be randomly allocated to one of four treatment groups (GWP42003-P 25 mg/kg/day, GWP42003-P 50 mg/kg/day, placebo 25 mg/kg/day dose volume equivalent, or placebo 50 mg/kg/day dose volume equivalent) at a 2:2:1:1 ratio. The placebo groups will be pooled for the analyses of efficacy.

If it is assumed that patients in the placebo group will experience a mean reduction in seizure frequency of 15% (from baseline), patients receiving GWP42003-P will experience at least a 50% reduction in seizures and a common standard deviation of 60%, then this sample size of 70 patients per group will be sufficient to detect a difference in response distributions with 90% power. This test is based on a two-sided non-parametric Wilcoxon-Mann-Whitney test for continuous response data with a 5% significance level.

Open-label Extension:

All patients who wish to continue on IMP following the blinded phase.

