2.2 Changes to the Proposed Sensitivity Analyses

The proposed sensitivity analyses have been changed as follows:

- Addition of the replaced primary analysis of Wilcoxon rank-sum test as a sensitivity analysis;
- Where appropriate, other sensitivity analyses using the Wilcoxon rank-sum test will now use the same method as the primary analysis (i.e., negative binomial regression).

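### The only MNAR sensitivity analysis listed never tests the primary rate ratio, and its imputation as worded can give negative seizure frequencies

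*Protocol*

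**What the plan says.** Protocol section 13.6.2 makes the primary analysis a negative binomial mixed model of baseline and treatment-period counts, with log reported days as offset. For a patient who withdraws, only data up to withdrawal are used.

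Section 13.6.2.1 then lists the sensitivity analyses. The last is the only one under MNAR. Its test is a "Wilcoxon rank-sum test on percentage change from baseline in number of seizures (average per 28 days) during the treatment period, using multiple imputation (MI").

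On scale it says: "MI will be performed on the seizure frequency, based on time points corresponding to each 14 calendar days of the treatment period". Intermittent gaps are filled by MCMC in SAS PROC MI, 100 times. Later gaps are filled by MONOTONE REG. Active-arm patients missing under MNAR are imputed with the placebo group as reference, in two scenarios: discontinuation for adverse events, and discontinuation for any reason. No transformation, lower bound or rounding is stated, and full details are left to the SAP.

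Amendment 6, which replaced the Wilcoxon test as the primary method, says of the others: "Where appropriate, other sensitivity analyses using the Wilcoxon rank-sum test will now use the same method as the primary analysis".

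**The concern.** There are two separate weaknesses.

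**The estimate the trial rests on is not stressed.** With available data and a days offset, the primary model lets a withdrawn patient's observed rate stand for the whole treatment period. The usual question is what happens to the rate ratio if patients who stop active drug revert to placebo-like rates. The listed MNAR analysis answers a different question, about ranks of percentage change. Amendment 6's own rationale prefers count modelling partly because percentage change can mislead for early withdrawals, and these are the patients the MNAR analysis is about.

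**The imputation model does not suit the variable.** MCMC and MONOTONE REG draw from normal distributions. Entry (criterion 6.1.11) requires at least eight seizures in 28 days and sets no upper limit, so a long right tail is expected. The same section log-transforms frequency, adding 1 where there are zeros, for the ANCOVA, but says nothing similar for the imputation.

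At stake is the credibility of the one analysis meant to show that the result does not depend on the withdrawal assumption.

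**Working it through.** **1. The plan's own figure.** Section 13.1 assumes a "mean reduction in seizure frequency of 15% (from baseline), patients receiving GWP42003-P will experience at least a 50% reduction in seizures", the same SD (60 percentage points) in every group, allocation "at a 2:2:1:1 ratio" with placebo pooled (70 per group), and a "two-sided non-parametric Wilcoxon-Mann-Whitney test for continuous response data with a 5% significance level".
- Probability that a random active patient does better: p = Φ(35/(60√2)) = Φ(0.4125) = 0.660.
- Noether power with 140 patients: Φ(√(3×140)×(0.660−0.5) − 1.96) = Φ(20.49×0.160 − 1.96) = Φ(1.32) = 90.6%.

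This reproduces the stated 90%. The point below does not affect it.

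**2. Which listed analyses cover informative withdrawal of the rate ratio?**
- Worst of LOCF, NOCB and mean: uses the primary model, but only for intermittent unreported diary days.
- Per-protocol set: completers only (section 13.3).
- Maintenance-period and 4-week analyses: primary model, observed data only.
- Rank ANCOVA, log ANCOVA and plain Wilcoxon: not the primary model, no imputation for withdrawal.
- MNAR analysis: addresses withdrawal, but by Wilcoxon.

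None combines the primary model with MNAR.

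**3. Why negatives arise.** MONOTONE REG draws from a normal distribution with predicted mean m and one residual SD s for all patients. P(draw < 0) = Φ(−m/s). With skewed data s is driven by high-frequency donors, while m is small for low-baseline patients, so the probability is not negligible.

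**4. Size, by simulation.** All inputs on skew and dropout are assumptions. The treatment period is 112/14 = 8 windows, with 70 placebo donors.

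| Assumed setting | Negative imputed windows | Withdrawn patients below −100% |
|---|---|---|
| Between-patient log-SD 0.9–1.3, within 0.4–0.5; withdrawal after window 1; two simulations | 15–26% and 15–24% | 8–19% and 9–19% |
| Median 30–100 per 28 days, log-SD 0.8–1.1, baseline ≥8; 10–20% of active arm withdrawn early or at random times | 23–29% | 7–20% |
| A further run with assumed skew and dropout | 17–28% | 7–17% |

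With withdrawal after window 4, the share below −100% drops to 3–6%.

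**5. Where withdrawn patients rank** (second row of the table, active and placebo combined):
- Best tenth: 20–28% with raw imputation, 9–12% with log(x+1), 14–20% with their own complete data.
- Worst tenth: 10–21%.
- Median rank: 0.42–0.52, where 0.50 is the middle.

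With no drug effect, the further run counted 23–28% of withdrawn patients as at least 50% improved, against about 15% of placebo patients and 13–15% under log(x+1) imputation.

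**6. Effect on the test.**
- Strong assumed effect: rejection in the six settings run both ways differed by at most 0.4 percentage points (for example 99.3% raw, 99.7% log). Power is near its ceiling here, so this check is insensitive.
- Weaker effect (median change −45% active, −25% placebo): rejection in favour of drug 73–97% raw against 80–99% log, with mean Z closer to zero on the raw scale in all six settings.
- No effect: false rejection in favour of drug 0.8–3.2% raw against 1.2–3.5% log, with a mean Z shift towards drug of at most 0.07.

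**The case against.** The strongest reply is that the bullet leaves full details to the SAP, and section 13.6.3 says further robustness analyses may be specified there. A transformation, a minimum value or an MNAR version of the primary model could all appear in it. That limits the claim to what the protocol lists. It does not remove it, because the bullet already fixes the imputed variable, the two normal-theory procedures, the reference group and the test.

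Three further replies stand:
- A rank test limits the influence of impossible values, and step 6 shows little change in the result.
- Keeping the Wilcoxon test does not contradict Amendment 6, whose wording is conditional on appropriateness.
- The analysis lies outside the testing hierarchy in Table 13.6-1.

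A reader might go further and infer that negative draws rank withdrawn patients as a group among the best responders, so that the analysis falsely supports robustness. Neither the documents nor the calculations support that. The spread widens at both ends, the typical withdrawn patient stays near the middle, and raw-scale imputation if anything slightly attenuates a drug effect.

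**Conclusion.** The point holds in two limited parts. First, no listed analysis examines the negative binomial rate ratio under informative withdrawal. This follows from the text alone. Second, the imputation as worded can give negative frequencies and reductions above 100%. The sizes, about 15–29% of imputed windows and about 7–20% of early-withdrawn patients, rest on assumed skew and dropout and shrink when withdrawal is later. A false favourable conclusion is not shown. The defect is an ill-fitting imputation model aimed at a different estimate from the primary one.

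**What to change.** Revise the MNAR bullet in section 13.6.2.1, and carry the change into the SAP:
- Impute 14-day counts from a negative binomial model, or impute log(frequency+1), for both the intermittent and the monotone steps, under the same placebo-reference rule. If the log scale is used, state the back-transformation, the floor at zero and the rounding to counts.
- Refit the primary negative binomial model to each completed data set and pool the log rate ratios by Rubin's rules.
- Report the rate ratios with 95% confidence intervals under both discontinuation scenarios.
- Keep the Wilcoxon version as supportive.

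Truncating raw draws at zero is not an adequate substitute. In the simulations it moved withdrawn patients' median rank to 0.62–0.73, against about 0.50, and left only 4–6% in the best tenth.

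The cost is extra programming before unblinding, by which time section 13.2 requires the blinded-phase SAP to be final. No data collection, sample size or hierarchy claim changes.

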13.6.3 Secondary Endpoint(s)

The following endpoints will be compared between treatment groups over the treatment period, for the blinded phase, and during the open-label extension phase relative to the pre-randomization baseline of the blinded phase:

Antiepileptic Efficacy Measures:

Key:

- Number of patients considered treatment responders defined as those with a $\geq 50\%$ reduction in seizure frequency (blinded phase only).
- Change in CGIC or SGIC score.
- Change in total seizures.

The hypothesis testing approach for controlling the Type I error for these endpoints are described in [Section 13.6](#) and Table 13.6-1.

Other:

- Percentage change from baseline in number of seizures (average per 28 days; OLE phase only).
- Number of patients considered treatment responders defined as those with a $\geq 25\%$, $\geq 50\%$ (OLE phase only), $\geq 75\%$ or 100% reduction in seizure frequency.
- Number of patients experiencing a $> 25\%$ worsening, -25 to $+25\%$ no change, 25–50% improvement, 50–75% improvement or $> 75\%$ improvement in seizure frequency.

Study Code: GWEP1521
EudraCT Number: 2015-002154-12
Protocol V8 23Apr19

- Change in number of seizure-free days.
- Change in number of ‘other’ seizures (absence, myoclonic, focal sensory and infantile/epileptic spasms).

Growth and Development (patients less than 18 years):

- Change in serum IGF-1 levels.
- Change in Tanner Staging score (for patients aged 10–17 [inclusive]).

Quality of Life:

- Changes in the QOLCE (patients 2–18 years) or QOLIE-31-P (patients 19+ years) score.
- Change in PGIC score.

Blinded Phase:

The number of patient responders (including the key secondary endpoint) and the number of patients seizure-free will be summarized and analyzed using a Cochran–Mantel–Haenszel test stratified by age group. In addition, the difference in proportions and the odds ratio, together with 95% CIs, comparing the treatment groups will be presented.

For number of seizure-free days, use of rescue medication, number of episodes of *status epilepticus* (only if there is a sufficient number of patients with data), Vineland-II, Wechsler scales, CBCL, ABCL, SCQ, QOLCE and QOLIE-31-P scores, the data will be summarized at baseline and over the treatment period, and at each time-point (or 28-day period, as appropriate) during the maintenance period. Changes from baseline to the average over the treatment period (or at end of study) will be analyzed using ANCOVA (or appropriate non-parametric methods if data are found to be not normally distributed). The models will include baseline and age group as covariates and treatment group as fixed factor. The treatment difference, together with the 95% CIs will be presented.

The changes in composite focal seizure score, change in total seizures, the number of seizures by subtype and the number of ‘other’ seizures will be analyzed using the same analysis as the primary endpoint.

SGIC-SD/CGIC-SD, SGIC/CGIC and PGIC assessments recorded at the end of treatment will be analyzed with ordinal logistic regression using the proportional odds model.

Study Code: GWEP1521
EudraCT Number: 2015-002154-12
Protocol V8 23Apr19

Changes from baseline for IGF-1 levels will be summarized by treatment group and plotted against the Tanner Stages, weight, and height.

Tanner Stages will be evaluated and summarized descriptively at each time-point in terms of frequency and proportions. Number (%) of patients with changes in Tanner Stages will be summarized by treatment group.

In order to explore the robustness of the primary analysis, further sensitivity analysis (in addition to that already detailed in [Section 13.6.2.1](#)) may be specified in the SAP.

Open-label Extension:

Secondary endpoints will be summarized across time, using appropriate statistical methods. Descriptive statistical methods will be used throughout. There will be no formal hypothesis testing.

Exploratory Endpoints:

Antiepileptic Efficacy Measures:

- Change in composite focal seizure score (frequency × severity).
- Change in number of seizures by subtype.
- Change in use of rescue medication.
- Change in the number of episodes of *status epilepticus* (convulsive and non-convulsive).
- Changes in duration of seizure subtypes as assessed by the Subject Global Impression of Change in Seizure Duration (SGIC-SD) or the Caregiver Global Impression of Change in Seizure Duration (CGIC-SD).

TAND:

Cognitive and Behavioral Function:

- Changes in Vineland Adaptive Behavior Scales, Second Edition (Vineland-II).
- Changes in Wechsler Scales (pre-school, primary, children, adult).
- Changes in Achenbach Child Behavior Checklist (CBCL) and Adult Behavior Checklist (ABCL).

Autistic Features:

- Change in Social Communication Questionnaire (SCQ) score.

Study Code: GWEP1521
EudraCT Number: 2015-002154-12
Protocol V8 23Apr19

PK (Blinded Phase Only):

- The plasma concentrations will be summarized by time window for CBD and its major metabolites following single and multiple doses of GWP42003-P. Where data allows, the area under the plasma concentration curve (AUC_{0-t}) from time zero to the last measurable time-point will be calculated.
- Plasma concentrations of concomitant AEDs before and after treatment with GWP42003-P, where available.

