
Statistical Considerations
	
Blinded Phase:
 
Each of the primary and secondary endpoints will be described and compared between treatment groups, using appropriate statistical methods, over the 16-week, double-blind maintenance and titration period.
 
Statistical hypothesis testing will be performed on the primary endpoint and other endpoints as appropriate. Each endpoint, including the primary will have 2 comparisons against placebo (25 mg/kg/day GWP42003-P and 50 mg/kg/day GWP42003-P vs. placebo). Also, 3 key secondary endpoints have been defined.
 
The primary and key secondary endpoints will be tested with their Type I error controlled by use of a hierarchical gate-keeping procedure. One must reject the null hypothesis of an endpoint at the level of 0.05 (2-sided) to test the hypothesis of the subsequent endpoint in the sequence at the level of 0.05 (2-sided). If a null hypothesis is not rejected then testing will stop and all subsequent analyses will be declared not statistically significant.
 
The secondary endpoints will be tested hierarchically, starting with the key secondary endpoints followed by all other and exploratory secondary endpoints. No multiplicity adjustments will be made for all other secondary endpoints.
 
All other statistical tests will be two-tailed and carried out at the 5% level of significance.
 
All safety data will be summarized using appropriate statistical methods.
 
Open-label Extension:
 
All data collected during this study will be summarized across

[figure not shown]
SPONSOR: GW RESEARCH LIMITED

Study Code: GWEP1521
EudraCT Number: 2015-002154-12
Protocol V8 23Apr19

	
time, using appropriate statistical methods. Where baseline data are available from the blinded phase, changes from baseline will also be presented.
 
Descriptive statistical methods will be used throughout. There will be no formal hypothesis testing.

Sponsor	
GW Research Ltd [name] United Kingdom

Study Code: GWEP1521
 EudraCT Number: 2015-002154-12
 Protocol V8 23Apr19

Figure 1-1 Study Design and Treatment Schema: Blinded Phase

[figure not shown]
* For patients not entering the open-label extension at Visit 10.

** For patients not entering the open-label extension; can be conducted by telephone.

Study Code: GWEP1521
 EudraCT Number: 2015-002154-12
 Protocol V8 23Apr19

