2.2 Secondary

Blinded Phase:

- To evaluate the effect of GWP42003-P compared with placebo on antiepileptic measures.
- To evaluate the effect of GWP42003-P on growth and development (in patients less than 18 years old) compared with placebo.
- To evaluate the effects of GWP42003-P on quality of life compared with placebo.
- To evaluate the safety and tolerability of GWP42003-P compared with placebo.

Open-label Extension:

- To evaluate the long term effects of GWP42003-P, as add-on therapy, on antiepileptic measures.
- To evaluate the long term effect of GWP42003-P on growth and development (in patients less than 18 years old).
- To evaluate the long term effects of GWP42003-P on quality of life.
- To evaluate the long term safety and tolerability of GWP42003-P.

Study Code: GWEP1521
EudraCT Number: 2015-002154-12
Protocol V8 23Apr19

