4.1.2 Secondary Endpoint(s)

Blinded Phase:

The following endpoints will be compared between treatment groups over the 16-week, double-blind treatment period (all changes relative to baseline):

Key:

- Number of patients considered treatment responders defined as those with a $\geq 50\%$ reduction in TSC-associated seizure* frequency.
- Change in Caregiver Global Impression of Change (CGIC) or Subject Global Impression of Change (SGIC) score.
- Change in total seizures.

Other:

Antiepileptic Efficacy Measures:

- Number of patients considered treatment responders defined as those with a $\geq 25\%$, $\geq 50\%$, $\geq 75\%$ or 100% reduction in TSC-associated seizure* frequency.
- Number of patients experiencing a $> 25\%$ worsening, $- 25$ to $+ 25\%$ no change, $25-50\%$ improvement, $50-75\%$ improvement or $> 75\%$ improvement in TSC-associated seizure* frequency.
- Change in number of TSC-associated seizure*-free days.
- Change in number of 'other' seizures (absence, myoclonic, focal sensory and infantile/epileptic spasms).

Growth and Development (in patients less than 18 years old):

Study Code: GWEP1521
EudraCT Number: 2015-002154-12
Protocol V8 23Apr19

- Change in serum insulin-like growth factor-1 (IGF-1) levels.
- Change in Tanner Staging score (for patients aged 10–17 [inclusive]).

Quality of Life:

- Changes in the Quality of Life in Childhood Epilepsy (QOLCE; patients 2–18 years) or Quality of Life in Epilepsy (QOLIE-31-P; patients 19+ years) score.
- Change in Physician Global Impression of Change (PGIC) score.

Safety and Tolerability:

- AEs.
- Clinical laboratory parameters.
- 12-lead electrocardiogram (ECG).
- Physical examination parameters (including height and weight).
- Vital signs.
- Columbia-Suicide Severity Rating Scale (C-SSRS; 19+ years) or C-SSRS Children's (6–18 years) score, where applicable.
- Number of inpatient hospitalizations due to epilepsy.
- Abuse liability.
- Effects on menstruation cycles (in females).

Open-label Extension:

The following endpoints will be assessed relative to the pre-randomization baseline of the blinded phase:

*TSC-associated seizures include: focal motor seizures without impairment of consciousness or awareness; focal seizures with impairment of consciousness or awareness; focal seizures evolving to bilateral generalized convulsive seizures and generalized seizures (generalized tonic-clonic, tonic, clonic or atonic) that are countable.

Key:

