13.6 Endpoints and Statistical Methods

Blinded Phase:

Statistical hypothesis testing will be performed on the primary endpoint and other endpoints as appropriate. Each endpoint, including the primary will have 2 comparisons against placebo (25 mg/kg/day GWP42003-P and 50 mg/kg/day GWP42003-P vs. placebo). Also, 3 key secondary endpoints have been defined.

Study Code: GWEP1521
 EudraCT Number: 2015-002154-12
 Protocol V8 23Apr19

The primary and key secondary endpoints will be tested with their Type I error controlled by use of a hierarchical gate-keeping procedure, in the sequence given in Table 13.6-1. One must reject the null hypothesis of an endpoint at the level of 0.05 (2-sided) to test the hypothesis of the subsequent endpoint in the sequence at the level of 0.05 (2-sided). If a null hypothesis is not rejected then testing will stop and all subsequent analyses will be declared not statistically significant.

Test	Endpoint	Treatment Comparison
1	Change from baseline in number of TSC-associated seizures	25 mg/kg/day GWP42003-P vs. Placebo
2	50% responder analysis	25 mg/kg/day GWP42003-P vs. Placebo
3	Change from baseline in number of TSC-associated seizures	50 mg/kg/day GWP42003-P vs. Placebo
4	50% responder analysis	50 mg/kg/day GWP42003-P vs. Placebo
5	Change in CGIC/SGIC	25 mg/kg/day GWP42003-P vs. Placebo
6	Change from baseline in total seizures	25 mg/kg/day GWP42003-P vs. Placebo
7	Change in CGIC/SGIC	50 mg/kg/day GWP42003-P vs. Placebo
8	Change from baseline in total seizures	50 mg/kg/day GWP42003-P vs. Placebo

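### The blinded-phase growth objective promises a comparison with placebo, but Section 13.6.3 gives change in IGF-1 only group summaries and plots, with no pre-specified treatment difference or interval

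*Protocol*

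**What the plan says.** **The promise.** Section 2.2 states the blinded-phase objective as "To evaluate the effect of GWP42003-P on growth and development (in patients less than 18 years old) compared with placebo". The growth objective for the open-label extension, in the same section, carries no reference to placebo.

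Section 4.1.2 lists change in serum IGF-1 and change in Tanner score, under growth and development, among the blinded-phase endpoints to be compared between groups. Section 13.6.3 opens its own endpoint list in the same way: "The following endpoints will be compared between treatment groups over the treatment period". Section 13.6 states that "Each endpoint, including the primary will have 2 comparisons against placebo", and the synopsis that "Each of the primary and secondary endpoints will be described and compared between treatment groups".

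**The method.** For IGF-1, Section 13.6.3 specifies: "Changes from baseline for IGF-1 levels will be summarized by treatment group and plotted against the Tanner Stages, weight, and height". For Tanner staging it specifies: "Tanner Stages will be evaluated and summarized descriptively at each time-point in terms of frequency and proportions", and then: "Number (%) of patients with changes in Tanner Stages will be summarized by treatment group".

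**The method for other endpoints in that section.** Seizure-free days, rescue medication, status epilepticus, Vineland-II, Wechsler, CBCL, ABCL, SCQ, QOLCE and QOLIE-31-P are to be analyzed by ANCOVA, or by a non-parametric method if the data are not normally distributed. The ANCOVA adjusts for baseline and age group and reports a treatment difference with a 95% interval. IGF-1 is not on that list. It is also not named in the Cochran-Mantel-Haenszel, negative binomial or proportional-odds analyses.

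**The concern.** The plan asks a comparative question about growth and then fixes an analysis that stops before the comparison. This is more than detail left to the SAP: the protocol names the IGF-1 method, and that method contains no contrast.

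The ordering is also hard to explain. Rescue medication, status epilepticus, Vineland-II, Wechsler, CBCL, ABCL and SCQ are classed as exploratory, yet they receive an adjusted difference with an interval. IGF-1 is a secondary endpoint under its own comparative objective and receives less.

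Every patient in the extension takes the drug, so the 16 blinded weeks hold this trial's only placebo-controlled IGF-1 data in children. If the method stays as written, anyone wanting the size of a dose-placebo difference must construct it afterwards, choosing the adjustment once the data are known.

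**Working it through.** **Step 1. Promise against method.**

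| Endpoint | Class | Comparison promised | Blinded-phase method in Section 13.6.3 |
|---|---|---|---|
| Change in IGF-1 | Secondary | Yes (2.2, 4.1.2, 13.6, 13.6.3) | Summary by group, plots |
| QOLCE / QOLIE-31-P | Secondary | Yes | Adjusted difference, 95% interval |
| Vineland-II, Wechsler, CBCL/ABCL, SCQ | Exploratory | TAND objective in 2.3 | Adjusted difference, 95% interval |

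The text for IGF-1 falls short of the promise made for it.

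**Step 2. Are the data there?** Appendix 1 schedules IGF-1 at Visits 3 and 10, and Sections 9.1.1.3 and 9.1.1.10 limit it to patients under 18. Baseline and end-of-treatment values are therefore collected, and age group is a randomization stratum (Section 7.2). Nothing new has to be measured.

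**Step 3. What does adjustment gain over raw change?** The protocol gives no IGF-1 variance or correlation, so there is no plan figure to reproduce. Assume equal variance σ² at both visits and correlation r between them.

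- Variance of raw change: 2σ²(1 − r)
- Residual variance after baseline adjustment: σ²(1 − r²)
- Ratio: (1 − r²) / [2(1 − r)] = (1 + r)/2

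| r (assumed) | (1 + r)/2 |
|---|---|
| 0.5 | 0.75 |
| 0.6 | 0.80 |
| 0.7 | 0.85 |
| 0.8 | 0.90 |

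Adjustment for baseline removes 10% to 25% of the variance of raw change over this range. This supports using ANCOVA for the contrast. It does not measure the gap itself, which is that no contrast is specified.

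**Step 4. Would the interval be informative?** Section 13.1 plans 70 patients per group. The share under 18 is not stated, so take 40% to 100%: 0.40 × 70 = 28, up to 70. In units of the IGF-1 SD, the half-width of a 95% interval for one dose against placebo is 1.96 × √[(2/k)(1 − r²)], where k is the number per group under 18.

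- k = 28, r = 0: 1.96 × √(2/28) = 0.52
- k = 42 (60% of 70), r = 0.5: 1.96 × √[(2/42) × 0.75] = 0.37
- k = 70, r = 0.7: 1.96 × √[(2/70) × 0.51] = 0.24

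These figures ignore missing samples and any gain from adjusting for age group. They show that a usable interval can be had from the planned sample, and nothing about the size of any effect.

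**The case against.** The strongest reply is that comparison is used loosely throughout this protocol. The lead-in in Section 4.1.2 also covers adverse events, laboratory values, ECG and vital signs. The safety objective in Section 2.2 is worded against placebo as well, and Section 13.6.5 answers it with tables by group. On that view IGF-1, a serum analyte, is handled like the other laboratory measures. This stands in part: it would be wrong to infer that IGF-1 is the only continuous secondary endpoint without a model, because laboratory values, vital signs, height and weight are also only summarized (Sections 13.6.5.3 and 13.6.5.4). But growth has its own objective apart from safety, and its method sits in Section 13.6.3, where the other continuous measures receive a treatment contrast.

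Three stronger readings are tempting and are not supported.

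- **That the objective cannot be answered at all.** Section 13.4 provides the number, mean and SD by group, from which a crude unadjusted difference and interval can be worked out. What is missing is a pre-specified, adjusted estimate.
- **That unadjusted IGF-1 change would be governed by the age and pubertal mix of each group.** The protocol gives no figures for this, and randomization is stratified by age. The planned plots against Tanner stage, weight and height already look at maturation.
- **That Tanner stage needs a formal contrast too.** It applies to ages 10 to 17, is followed here for 16 weeks, and need not be re-examined once stage V is reached (Section 9.2.14). Description is defensible.

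The SAP is not at hand and may add a contrast. The protocol's method would still fall short of its own objective.

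**Conclusion.** The point holds for IGF-1. The protocol promises a comparison with placebo for change in IGF-1 in patients under 18 and specifies no treatment difference or interval for it, while giving one to exploratory scales in the same section.

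Its weight is modest. IGF-1 is not a key secondary endpoint, lies outside the hierarchy in Table 13.6-1 and supports no formal claim. The mismatch rests on the text alone. The variance ratio of 0.75 to 0.90 depends on an assumed correlation of 0.5 to 0.8 and equal variances. The half-width of about 0.24 to 0.52 SD depends on an assumed 28 to 70 patients per group under 18 and a correlation of 0 to 0.7.

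**What to change.** Add change in serum IGF-1 from Visit 3 to Visit 10, in patients under 18, to the existing ANCOVA list in Section 13.6.3. Use baseline IGF-1 and randomization age group as covariates and treatment as the fixed factor, as for the other endpoints on that list. Present each dose-placebo difference with its 95% confidence interval, labelled nominal and outside the hierarchy. Keep the summaries and plots as support, and leave Tanner staging descriptive.

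The cost is a sentence of protocol or SAP wording and one extra table, with no new samples or visits. If the sponsor means growth to be descriptive only, the objective in Section 2.2 and the lead-ins in the synopsis and Sections 4.1.2, 13.6 and 13.6.3 should say so. That removes the contradiction but still leaves the controlled IGF-1 data without a planned estimate.
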